## Statistical Analysis Plan

---

## **Statistical Analysis Plan**

---

### **1 PURPOSE**

The purposes of this Statistical Analysis Plan (SAP) is to describe the statistical methodology that will be used to confirm the safety and effectiveness of the Omnipod Horizon™ Automated Glucose Control System in patients with type 1 diabetes. Should there be any discrepancy between the study protocol and this SAP, the content of the SAP shall prevail.

### **2 STUDY DESIGN**

#### **2.1 STUDY DESIGN OVERVIEW**

This is a single-arm, multi-center, prospective clinical study. The study will be conducted in 6-8 clinical study sites in the United States. The study is expected to enroll up to 48 subjects in order to obtain 36 evaluable subjects with 18 subjects in each of two age cohorts (6-13.9 years and 14-70 years of age).

#### **2.2 INVESTIGATIONAL DEVICE**

The Omnipod Horizon™ Automated Glucose Control System (“Horizon™ System”) is comprised of three primary components:

- Omnipod Horizon™ tubeless, insulin delivery alternate controller enabled (ACE) pump (Pod)
- Omnipod Horizon™ Personal Diabetes Manager (PDM) which is a Samsung J3 locked down android device that operates the Omnipod Horizon™ App
- Dexcom G6 - Continuous Glucose Monitoring (CGM) system

In addition, the following non-investigational, commercially available devices will be used during the study:

- Contour® Next One blood glucose meter (Ascensia Diabetes Care, [name])
- Precision Xtra ketone meter (Abbott Diabetes Care Inc., [name])

#### **2.3 STUDY SCHEDULE**

The study will consist of 14-day standard therapy (ST) phase and a 14-day hybrid closed-loop (HCL) phase. Following the ST phase, subjects will be divided into 2 groups. Group 1 subjects (N=16; 8 subjects in each age cohort) will participate in the HCL phase for the first 2 days while in the supervised hotel/rental house environment and then transition to the 12-day outpatient setting. The Group 2 subjects (n=20; 10 subjects in each age cohort) will participate in the HCL phase in a 14-day outpatient setting.

The Horizon™ System has two modes. In manual mode, the system will function equivalently to

## **Statistical Analysis Plan**

---

the Omnipod DASH System. This includes delivering insulin at programmed basal rates and bolus amounts with the option to set temporary basal profiles. In automated mode, the system will support the use of multiple target glucose values. The programmed basal rates, glucose targets and bolus calculator settings will inform the MPC algorithm for insulin dosing parameters.

### **2.4 TARGET BLOOD GLUCOSE CHALLENGES**

All subjects take part in the prescribed target blood glucose (BG) challenges for approximately 72 consecutive hours each:

- Target BG of 130 mg/dL during HCL days 1-3
- Target BG of 140 mg/dL during HCL days 4-6
- Target BG of 150 mg/dL during HCL days 7-9
- Target BG of subject's choosing of 110-150 mg/DL during HCL days 10-14

### **2.5 STUDY SUCCESS**

There are no pre-specified criteria that are evaluated to consider the study a success. An independent Data Safety Monitoring Board (DSMB) will evaluate the study progress with respect to safety and determine whether the enrollment of pivotal subjects may proceed.

### **2.6 RANDOMIZATION**

This is a single-arm, multicenter, prospective clinical study where all eligible subjects will use the investigation device. Subjects will not be randomized.

### **2.7 POINT OF ENROLLMENT**

A subject is enrolled in the study upon placement of the first study CGM. Subjects that do not meet the eligibility criteria will not continue in the study and will be considered screen failures.

## **3 STUDY OBJECTIVES AND ENDPOINTS**

### **3.1 SAFETY OBJECTIVES AND ENDPOINTS**

The primary safety objective is to evaluate the safety of the Omnipod Horizon™ Automated Glucose Control System in patients with type 1 diabetes. The safety objective will be evaluated by summarizing the following endpoints during HCL:

- Primary safety endpoint:
  - Proportion of subjects with serious device-related adverse events
- Secondary safety endpoints:
  - Proportion of subjects with severe hypoglycemia
  - Proportion of subjects with diabetic ketoacidosis (DKA)

## Statistical Analysis Plan

### 3.2 PRIMARY EFFECTIVENESS OBJECTIVE AND ENDPOINT

The primary effectiveness objective is to evaluate the effectiveness of the Omnipod Horizon™ Automated Glucose Control System. The primary effectiveness objective will be evaluated by summarizing the following:

- Percentage of time in range 70-180 mg/dL during hybrid closed-loop (HCL) compared to standard therapy (ST) for
  - Target BG challenge days (approximately HCL days 1-9)
  - Non-challenge days (approximately HCL days 10-14)
  - Overall (HCL days 1-14)

### 3.3 SECONDARY EFFECTIVENESS OBJECTIVE AND ENDPOINTS

The secondary effectiveness objective is to evaluate additional glycemic measures of effectiveness of the Omnipod Horizon™ Automated Glucose Control System. The secondary objective will be evaluated based on the following per subject endpoints:

- Glucose metrics from system CGM during the hybrid closed-loop phase will be compared to the standard therapy phase during the day, overnight, and overall:
  - Mean glucose
  - Percentage of time in range 70-180 mg/dL
  - Percentage of time in range 70-140 mg/dL
  - Percentage of time in range > 180 mg/dL
  - Percentage of time in range  $\geq$  250 mg/dL
  - Percentage of time in range  $\geq$  300 mg/dL
  - Percentage of time in range < 70 mg/dL
  - Percentage of time in range < 54 mg/dL
  - Standard deviation
  - Coefficient of variation
- Glucose management indicator (GMI) based on overall mean glucose
- Percentage of time in hybrid closed-loop as proportion of overall device usage time
- Insulin requirements during the hybrid closed-loop phase will be compared to the standard therapy phase:
  - Total daily insulin (TDI) (units, units/kg)
  - Total daily basal insulin (units, units/kg)
  - Total daily bolus insulin (units, units/kg)

## 4 ANALYSIS OF PRIMARY EFFECTIVENESS ENDPOINTS

The primary effectiveness objective will be evaluated by summarizing the following:

## Statistical Analysis Plan

- Percentage of time in range (TIR) 70-180 mg/dL during hybrid closed-loop (HCL) compared to standard therapy (ST) for
  - Target BG challenge days (approximately HCL days 1-9)
  - Non-challenge days (approximately HCL days 10-14)
  - Overall (HCL days 1-14)

### 4.1 SAMPLE SIZE

This is a single-arm, multi-center, prospective study. The sample size is not hypothesis-driven and was chosen to provide adequate information on the investigational device's safety and performance. As such, the study plans to enroll up to 48 subjects to obtain a minimum of 36 evaluable subjects equally distributed across two age cohorts (6-13.9 years and 14-70 years).

### 4.2 PRIMARY ANALYSIS

There are no pre-specified hypotheses associated with the primary effectiveness endpoints. Summary statistics will be presented by age cohort for all endpoints, stratified by time points of interest (e.g., day, night, overall). The primary effectiveness endpoints will be summarized for modified Intention to Treat (mITT) and Per Protocol (PP) analysis sets, where the percentage of TIR during ST phase will be compared to the percentage of TIR during HCL BG challenge days, HCL non-challenge days, and over the entire HCL.

Since the target BG challenges require a specific setpoint, the start of the challenge will be the first record at the given setpoint, and the end of the challenge will be last record at the same setpoint.

All statistical comparisons will be conducted at a two-sided significance level of 5% using a paired t-test. If the assumptions for parametric test are grossly violated, a non-parametric method such as Wilcoxon signed rank test may be used. Since the results of endpoint analyses will not be used to support clinical claims, no adjustment for multiplicity will be performed.

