### Automated Mode

In Automated Mode, the system will support the use of multiple target glucose values, currently intended to be 110-150 mg/dL at commercialization, in 10 mg/dL increments. The experience for the user will reflect current setup flows whereby the health care provider assists the user to program basal rates, glucose targets and bolus calculator settings. These in turn will inform the MPC algorithm for insulin dosing parameters. The insulin dosing parameters will be adapted over time based on the total daily insulin (TDI) delivered during each Pod use. A temporary hypoglycemia protection mode (Hypo Protect) may be implemented by the user for various time durations during Automated Mode. With Hypo Protect, the algorithm reduces insulin delivery and is intended for use over temporary durations when insulin sensitivity is expected to be higher, such as during exercise.

The Omnipod Horizon™ System will include two apps on a locked-down smartphone (the Samsung J3), referred to as Personal Diabetes Manager (PDM): the Horizon App and the Dexcom App. The Horizon App, which will have a similar interface to the cleared Omnipod® DASH System (K191679), will allow the use of large text, graphics, and on-screen instructions to prompt the user through set-up processes. It will also be used to program the user's custom basal insulin delivery profile, check the Pod status, initiate bolus doses of insulin, make changes to a patient's insulin delivery profile, handle system alerts and alarms, and enter Automated Mode.

The Dexcom App interface is identical to the current app of the interoperable Dexcom G6 Continuous Glucose Monitoring System (K191450) and will provide CGM data, alerts, and alarms to the user.

The Horizon App and Dexcom App will not directly communicate with one another. Instead, the iCGM transmitter will communicate EGV (estimated glucose values) directly to the Pod. The Dexcom transmitter number must be entered into the Horizon App, and this information is sent to the Pod to allow transmission of EGV. The Pod will pair directly to the transmitter to receive EGV for the algorithm and also sends the EGV back to the Horizon App as shown in Figure 1.

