### 9.1 Target BG Challenges

All subjects will take part in the target blood glucose (BG) challenges (Table 4: Target BG Challenges). Following the commencement of the hybrid closed-loop phase, subjects will be required to set their target BG to 130 mg/dL for approximately 72 hours for days 1-3, 140 mg/dL for days 4-6, and 150 mg/dL for

day 7-9 according to Table 4: Target BG Challenges. Upon completion of the 3 target BG challenges (130 mg/dL, 140 mg/dL, and 150 mg/dL), subjects may choose their desired target BG between 110-150 mg/dL for the remainder of the 5-days of the hybrid closed-loop phase.

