**Table 4: Target BG Challenges**

	Days									
	1	2	3	4	5	6	7	8	9	10-14
Target BG	130 mg/dL			140 mg/dL			150 mg/dL			110-150 mg/dL

These settings will be reviewed by clinical staff at scheduled visits and through the remote monitoring system to ensure the requirements are met. If the requirements have not been met, clinical staff may request the subject adjust their setpoint until the requirements are met unless there are safety concerns.

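### SAP 4.2 ends each target-glucose challenge at the last record at its setpoint, with no tie to the scheduled challenge period, so free-choice days at 130, 140 or 150 mg/dL are counted as challenge days

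*SAP*

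**What the plan says.** The primary effectiveness endpoint is percentage of time in range 70-180 mg/dL, compared with standard therapy for challenge days, non-challenge days and all 14 hybrid closed-loop days (SAP 3.2 and 4).

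- **Schedule.** SAP 2.4 sets 130 mg/dL on days 1-3, 140 on days 4-6 and 150 on days 7-9, with "challenges for approximately 72 consecutive hours each". It then gives a target of the subject's "choosing of 110-150 mg/DL during HCL days 10-14".
- **Free choice.** Protocol 9.1 agrees: "subjects may choose their desired target BG between 110-150 mg/dL for the remainder of the 5-days of the hybrid closed-loop phase".
- **Endpoint label.** SAP 4 describes the second period as "Non-challenge days (approximately HCL days 10-14"), so the split is stated only approximately.
- **Boundary rule.** SAP 4.2 starts a challenge at the first record at its setpoint, and "the end of the challenge will be last record at the same setpoint". No other sentence in either document assigns individual CGM records to a period.
- **Movable dates.** Under Table 4 in Protocol 9.1, "clinical staff may request the subject adjust their setpoint until the requirements are met", unless there are safety concerns. A subject's challenges can therefore run past the nominal days.

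**The concern.** The boundary rule works only if a challenge setpoint is never used again once its challenge is over. The free-choice period allows exactly that. A subject who simply leaves the device at 150 after day 9 never leaves the 150 window. A subject who goes back to 130 stretches the 130 window across the 140 and 150 challenges and all free-choice days up to the last such record, including any days at 110 or 120.

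Two things follow. The challenge-day summary takes in days on which no challenge was prescribed. The non-challenge summary loses records or whole subjects, and those who keep full data are mainly the ones who chose 110 or 120. It is then selected on the target setting, which itself bears on time in range. SAP 7.5 plans no imputation, so a subject with no non-challenge records drops out of that paired comparison.

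**Working it through.** **Inputs**
- Three challenges of about 72 hours (SAP 2.4) and a 14-day closed-loop phase.
- CGM records about every 5 minutes (SAP 6.2): 24 × 60 / 5 = 288 per day.
- Selectable targets: Protocol 2.1.1 (Automated Mode) gives a range "currently intended to be 110-150 mg/dL at commercialization, in 10 mg/dL increments". If the study device uses the same steps, the targets are 110, 120, 130, 140 and 150, and 3 of the 5 are challenge setpoints.
- 36 evaluable subjects, 18 per age cohort (SAP 4.1).

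**The plan's own split.** 3 × 72 / 24 = 9 challenge days (9 × 288 = 2,592 possible records). 14 − 9 = 5 non-challenge days (5 × 288 = 1,440). This matches the labels in SAP 4.

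**The SAP 4.2 rule applied day by day.** Days 1-9 follow the schedule. Challenge days are the union of the three windows. The last column takes the narrower reading, in which a challenge ends when its first unbroken run at the setpoint ends.

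| Target on days 10-14 | Challenge / non-challenge days, rule as written | Free-choice share of challenge days | Unbroken-run reading |
|---|---|---|---|
| 110 or 120 throughout | 9 / 5 | 0% | 9 / 5 |
| 130 throughout | 14 / 0 | 5/14 = 35.7% | 9 / 5 |
| 140 throughout | 14 / 0 | 35.7% | 9 / 5 |
| 150 throughout | 14 / 0 | 35.7% | 14 / 0 |
| 110, then 130 on day 14 only | 14 / 0 | 35.7% | 9 / 5 |
| 120, with 130 on day 12 only | 12 / 2 | 3/12 = 25.0% | 9 / 5 |
| 150 on day 10, then 110 | 10 / 4 | 1/10 = 10.0% | 10 / 4 |

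Windows also overlap under the rule as written. With 130 throughout, the 130 window is days 1-14, so days 4-9 (6 days) lie in two windows. With 140 throughout, its window is days 4-14, so days 7-9 (3 days) do. With 150 there is no overlap.

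**Effect on the summaries.** Let q be the share of subjects with all five free-choice days misallocated, and D the difference in time in range between the free-choice and challenge periods. The documents give neither, so both are assumptions shown over a range.

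- Subjects keeping non-challenge data = 36(1 − q), or 18(1 − q) per cohort.
- Standard error factor for the non-challenge mean = √(1/(1 − q)), assuming an unchanged between-subject SD.
- Shift in the challenge-day mean = q × 5/14 × D, assuming equal record counts per day.

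| q | Of 36 | Of 18 per cohort | SE factor | Shift for D = 10 points |
|---|---|---|---|---|
| 0.2 | 28.8 | 14.4 | 1.12 | 0.7 |
| 0.4 | 21.6 | 10.8 | 1.29 | 1.4 |
| 0.6 | 14.4 | 7.2 | 1.58 | 2.1 |
| 1 | 0 | 0 | – | 3.6 |

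At q = 0.4, D = 5 gives 0.4 × 5/14 × 5 = 0.7 points, and D = 15 gives 2.1.

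**The case against.** The best counter-argument is that SAP 4.2 should be read together with SAP 2.4. A challenge is already described there as about 72 consecutive hours on named days. Protocol 9.1 opens free choice only once the three challenges are complete, so a completed challenge cannot contain free-choice records. A 14-day challenge overlapping the others is plainly not what the authors meant. On that view a careful analyst would stop each window at the end of its scheduled run.

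The intent is indeed clear, but the limit is not stated. The durations and day ranges are approximate. The check at Visits 7-9 (Protocol 9.6) is for at least 72 hours, which is a floor. Because challenge dates can move, a programmer cannot simply cut at day 9 and must fall back on the rule in 4.2. Two programmers could derive different primary summaries from the same log. The unbroken-run reading clears the 130 and 140 cases, but a subject who stays at 150 after day 9 is still misallocated, and 150 is the setting in place when free choice begins.

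Three further points stand. Under the narrower reading, q covers only subjects who stay at 150. D may be small for them, since their target does not change after day 9, so the shifts above illustrate scale and do not predict it. Finally, no decision hangs on the result: SAP 2.5 says "There are no pre-specified criteria that are evaluated to consider the study a success", SAP 4.2 states no hypotheses, and the overall summary is untouched.

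**Conclusion.** The concern holds. Followed as written, SAP 4.2 gives up to 14 challenge and 0 non-challenge days where the plan intends 9 and 5. It does so for three of the five selectable free-choice targets, if the study device uses 10 mg/dL steps. The day counts follow from the text and the nominal schedule alone. The effect on the summaries depends on the unknown q and D. For q from 0.2 to 0.6, about 29 down to 14 of 36 subjects would keep non-challenge data, and D = 10 points would shift the challenge mean by 0.7 to 2.1 points. The rule should be corrected before analysis because it governs two of the three primary effectiveness summaries. It does not undermine the trial.

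**What to change.** Amend SAP 4.2 before analysis so that:

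1. Each challenge starts at the first record at its setpoint, taken in the prescribed order 130, 140, 150.
2. Each challenge ends at the last record at that setpoint within the subject's own challenge period, before free choice begins. That period is about 72 hours, as in SAP 2.4, plus any documented extension under Protocol 9.1. The SAP should fix the exact cut-off. For a subject who stays at 150 the setpoint log shows no change, so the end must come from the 72-hour point after the first record at 150 or from a recorded date.
3. Each record belongs to one period only.
4. Non-challenge means all closed-loop records after the 150 mg/dL challenge period ends, whatever the setpoint.

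Under the nominal schedule this returns 9 and 5 days, with no overlap, for all five free-choice targets. The cost is two or three SAP sentences, a small change to the derivation program and one challenge end date per subject, recorded or derived. No visits or measurements are added, and what subjects do is unchanged.

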### 4.3 SUBGROUP ANALYSES

As described in this document, results will be stratified by phase of the study (ST versus HCL), age group (subjects aged 6-13.9 years versus subjects aged 14-70 years) and day versus night (daytime: 6AM to <12AM; nighttime as 12AM to <6AM). There are no plans to perform analyses separately for Group 1 and Group 2. Results for other subgroups may be presented as appropriate.

## 5 ANALYSIS OF SAFETY

All adverse events reported during the study will be reviewed and adequately reported to comply with applicable regulations. All reportable AEs will be assessed by the investigator who will determine whether the event is related to the study procedures or related to the study device, and

## Statistical Analysis Plan

whether the event meets any of the criteria for seriousness. The event will be considered serious if the event meets at least one criterion for seriousness.

### 5.1 MEDICAL MONITOR

An independent Medical Monitor will be responsible for individual and timely review of adverse events. The Medical Monitor will also adjudicate all serious adverse events (SAEs), including events of severe hypoglycemia and diabetic ketoacidosis, as well as all device-related adverse events for seriousness, severity, relationship to study device and procedure, whether the event is anticipated or unanticipated, and event categorization. The adjudication decision by Medical Monitor will be used for the final classification of adverse events for regulatory reports, product labeling, and publications or presentation.

### 5.2 RELATIONSHIP TO STUDY DEVICE AND PROCEDURE

The causal relationship to the study procedures and the investigational device for each adverse event will be rated as follows:

- Unrelated: The event is not related to the procedures or the investigational device.
- Possibly Related: The temporal sequence is such that the relationship is not unlikely or there is no contradicting evidence that can reasonably explain the subject's condition. There is a possibility of any relation between the event and the procedures or the investigational device.
- Related: The temporal sequence is relevant or the event abates upon completion of the procedure/ investigational device, or the event cannot be reasonably explained by the subject's condition or comorbidities. The event is related or most likely associated with the procedures or the investigational device.

For the purposes of dichotomizing the causal relationship in safety summaries, events that are “Related” or “Possibly Related” will be considered related.

### 5.3 SEVERITY

The severity of the adverse event will be rated based upon the following grades:

- Mild: Usually transient, requires no special treatment, and does not interfere with the participant's daily activities
- Moderate: Usually causes a low level of inconvenience, discomfort or concern to the participant and may interfere with daily activities, but is usually ameliorated by simple therapeutic measures and participant is able to continue in study

## Statistical Analysis Plan

- Severe: Interrupts a participant's usual daily activities, causes severe discomfort, may cause discontinuation of study device, and generally requires systemic drug therapy or other treatment

### 5.4 ANALYSIS OF ADVERSE EVENTS

Safety summaries and analyses will be based on all subjects that are enrolled in the study (i.e., Intention to Treat analysis set). All adverse events reported over the course of the study will be summarized and tabulated by study phase (standard therapy or HCL), event category, seriousness, severity, and relationship to the study procedures and the investigational device. Except where indicated, a subject reporting the same adverse event more than once will be counted once when calculating the number and percentage of subjects with that particular event. Adverse Event outcomes will be assessed descriptively as opposed to inferentially.

Adverse events leading to death or to discontinuation from the study will be listed separately. A listing of all adverse events will be provided. No formal tests of hypotheses are proposed for the safety endpoints.

